11.1 PERMANENT TREATMENT DISCONTINUATION WITH INVESTIGATIONAL MEDICINAL PRODUCT(S)

11.1.1 List of Criteria for Permanent Treatment Discontinuation

Patients may withdraw from treatment with IMP if they decide to do so, at any time and irrespective of the reason, or this may be done at the discretion of the Investigator. All efforts should be made to document the reason for discontinuation and this should be documented in the e-CRF.

Treatment with the IMP should be discontinued in any of the following cases:

- At the patient's request, at any time and irrespective of the reason (consent's withdrawal).
- If, in the Investigator's opinion, continuation of the study treatment would be detrimental to the patient's wellbeing, such as:
 - Disease progression.
 - Unacceptable AE.
 - Poor compliance to the study protocol.
 - Any other reason such as intercurrent illness that prevents further administration of study treatment (will be specified).
- Patient is lost to follow-up.
- Sponsor decision to discontinue the study.

If patients are clinically stable, and possibly deriving clinical benefit from therapy with minimal toxicity, the patient will be maintained on treatment for the maximum period of time defined in [Section 6.6.3](#).

11.1.2 Handling of Patients after Permanent Treatment Discontinuation

All permanent treatment discontinuation should be recorded by the Investigator in the appropriate screen of e-CRF when considered as confirmed. After study treatment is discontinued, patients should complete a follow-up visit 30 days after the last administration of the IMP as described in [Section 12.4](#).

Patients who have been withdrawn from the study treatment cannot be re-entered into the study.

11.1.3 Temporary Treatment Discontinuation with Investigational Medicinal Product(s)

Temporary treatment discontinuation may be considered by the Investigator because of suspected AEs. Reinitiation of treatment with the IMP will be done under close and appropriate clinical/and or laboratory monitoring once the Investigator has deemed it appropriate according to his/her best medical judgment and considers that the causality of the AE was unlikely related to the IMP(s). The patient must continue to meet the safety related selection criteria (refer to [Section 7.2](#) and [Section 7.3](#)).

For all temporary treatment discontinuations, the duration of the discontinuation should be recorded by the Investigator in the appropriate pages of the e-CRF.

11.2 REPLACEMENT OF PATIENTS

During the Phase I part of the study, a patient may be considered not evaluable for DLT and may be replaced at the same dose level as described in [Section 6.3](#).

Patients treated in the Phase II part of the study who are withdrawn from study treatment will not be replaced.

12 STUDY PROCEDURES

12.1 VISIT SCHEDULE

During the course of the study, all patients entering the study must be evaluated according to the schedule outlined in the flow charts in [Section 1](#) and described below. The results of the evaluation will be recorded in the e-CRF pages until the patient is not followed anymore. After the screening/ baseline visit, all eligible patients included in the study will have a visit on site as detailed below. A complete visit will be performed at EoT (30 days +/- 7 days after the last administration of the IMP). The patients will be followed until recovery or consolidation of any SAE or IMP-related AE. Additionally, ADA samples are required (60 days +/- 7 days after last IMP administration).

12.2 BASELINE EVALUATION

The pretreatment examinations are to be performed within 21 days (unless specified otherwise) prior to the first administration of the IMP. The informed consent form will have to be signed by the patient before any procedure specific to the study can be performed. The following assessments are to be performed at this visit.

If the patient cannot be registered within 21 days of informed consent, the same patient may be re-screened after discussion with the sponsor, provided that there are no persisting safety concerns for patient's study participation. The informed consent form will have to be re-signed by the re-screened patient before starting re-screening procedures. New patient number will be given for the re-screened patients.

- Inform to the registration center
- Medical History and Clinical Examinations:
 - Demography: Includes date of birth, gender and race.
 - Medical/Surgical History: includes relevant history of previous/associated pathologies other than multiple myeloma.
 - Disease History: includes date of initial diagnosis of MM, subtype, stage of international staging system (see [Appendix F](#)), previous anti-MM therapy (drug name by line of therapy, start and end date of administration, reason for discontinuation, best response and date of progression/relapse), disease status at inclusion (refractory to last IMiD or PI included therapy). In addition, results of additional procedures (such as karyotype, fluorescence in situ hybridization (FISH), etc.) performed as part of standard of care to assess the current disease status may also be collected.
 - Physical Examination: consists of examination of major body systems including neurological, digestive, extramedullary myeloma localizations, respiratory, hepatomegaly, splenomegaly, lymphadenopathy.
 - Weight and Height
 - Vital signs: includes heart rate, temperature, respiratory rate, blood pressure.

- Performance Status (ECOG)
- Prior medications given within 7 days prior to first dose.
- Adverse events/serious adverse events are to be reported from the signing of the informed consent.
- 12-lead ECG
- 2-D Echocardiogram or Multigated Acquisition (MUGA) scan
- Chest X-ray
- Laboratory Assessments:
 - Hematology: includes hemoglobin, hematocrit, RBC, WBC with differential, Mean Corpuscular Volume (MCV) and platelet count.
 - Serum Chemistry: includes SGOT (AST), SGPT (ALT), bilirubin (total and direct), alkaline phosphatase, lactate dehydrogenase (LDH), fasting glucose, sodium, potassium, chloride, magnesium, calcium/ corrected serum calcium, phosphate, uric acid, blood urea nitrogen (BUN), serum creatinine and eGFR (Revised equations for eGFR in Japanese), albumin and total protein.
 - Coagulation: includes PT or INR, and aPTT.
 - Urinalysis: includes blood, protein, glucose, pH, ketones, bilirubin, leucocytes, nitrates and specific gravity.
 - Pregnancy Test: women of child bearing potential must have a negative serum pregnancy test result within 7 days prior to first IMP administration.
 - HBs-Ag, HBc-Ab, HBs-Ab, HCV-Ab tests. If HBc-Ab and/or HBs-Ab positive at baseline, HBV-DNA test is required prior to registration. If history of HBV infection is suspected, monitoring of HBV-DNA is recommended on Day 1 of each cycle.
 - HIV-Ab tests (Testing is not required unless there is a suspicion of virus infection.)
- Disease Assessment:
 - Myeloma-specific Lab Tests:
 - M-protein quantification (serum electrophoresis and immunofixation and 24-hour urine collection for Bence Jones protein with urine electrophoresis and immunofixation)
 - Serum free light chain levels
 - Serum β 2-microglobulin
 - Immunoglobulins: IgG, IgA, IgM, IgD and IgE
 - Corrected serum calcium
 - Bone marrow aspiration to be performed.
In case of dry-tap, bone marrow biopsy to be performed.
(For subsequent cycle, only required to confirm a CR)
 - Extramedullary Disease: Radiologic imaging (CT/MRI scan) of plasmacytoma.

- Skeletal survey: X-ray.
X-ray skeletal survey should include radiographs of the following: lateral skull; Postero-Anterior (PA) chest; Antero-Posterior(AP) and lateral cervical spine; AP and lateral thoracic spine; AP and lateral lumbar spine; AP pelvis; AP upper extremities, shoulder to elbow, bilateral; and AP lower extremities, hip to knee, bilateral.
- Biomarker/ Exploratory Studies:
 - CD38 Receptor Density in bone marrow.
 - Cytogenetics/FISH in screening/ baseline bone marrow sample. Probes for fluorescence in situ hybridization (FISH) analysis may include t(4;14), t(14;16) and del(17p).
 - Immune phenotyping (bone marrow).
 - MRD assessment in bone marrow: baseline sample will be used as reference to determine major disease clone(s).
(For subsequent cycle, only required to confirm a CR)

All patients who signed the study informed consent form will be assigned a patient number. Each patient will receive an incremental identification number corresponding to his/her order of enrollment in the study. Those patients, who meet all the inclusion criteria and none of the exclusion criteria, will be eligible for registration in the study. A written confirmation of each eligible patient identification and treatment dose level will be forwarded to the Investigator.

12.3 DURING THE TREATMENT PERIOD

See flow charts in [Section 1.4](#) and [Section 1.5](#)

12.3.1 Day 1 of Each Cycle

All patients who are going to continue study treatment after completing Cycle 1 must sign a second ICF before commencing IMP administration. (Phase I part Cycle 2 only)

The evaluations below are to be performed prior to first IMP administration on Day 1 of each cycle unless otherwise indicated.

- Inform to the registration center (Cycle 1 only)
- Patient Registration (Cycle 1 only)
- Clinical Examinations:
 - Physical Examination
 - Performance Status (ECOG)
 - Weight
 - Vital signs
(to be taken pre-infusion, mid-infusion (when half the volume is administered), and end-infusion on days of IMP administration. If the infusion rate changes because of an

infusion-associated reaction, vital signs should be monitored every hour and at the end of the infusion.)

- AE/ SAE assessment
- Concomitant Medications
- Laboratory Assessments:
 - Hematology
(not required to be repeated at Cycle 1 Day 1 if screening labs were performed within 3 days prior to first IMP administration)
Perform direct and indirect coombs tests prior to the first IMP administration.
 - Serum Chemistry
(not required to be repeated at Cycle 1 Day 1 if screening labs were performed within 3 days prior to first IMP administration)
 - If history of HBV infection is suspected, perform HBV-DNA test on Day 1 of each cycle.
 - Urinalysis: Quantitative urinalysis will be needed if hematuria is observed or clinically indicated.
(not required to be repeated at Cycle 1 Day 1 if screening labs were performed within 3 days prior to first IMP administration)
 - Pregnancy Test: Not required at Cycle 1 Day 1 if a negative serum pregnancy test result available within 7 days prior to first IMP administration. Urine test can be used at Day 1 of each subsequent cycle.
 - In case of viral reactivation during study treatment (greater than $1 \log_{10}$ IU/mL increase in HBV DNA or reappearance of HBsAg or detection of HBV DNA in patients with resolved infection), ALT and AST will be closely monitored every month up to study treatment discontinuation. HBV DNA to be done as per specialist advice (Phase II part, Subsequent Cycles only).
- Disease Assessment:
 - Myeloma-specific Lab Tests:
(not required to be repeated at Cycle 1 if screening labs were performed within 3 days prior to first IMP administration)
 - M-protein quantification (serum and 24-hours urine)
 - Serum β 2-microglobulin to be performed if clinically indicated
 - Immunoglobulins: IgG, IgA and IgM (IgD or IgE test to be performed if positive at baseline)
 - Corrected serum calcium
 - Serum and urine immunofixation and free light chain tests to be performed to confirm a CR and as clinically indicated.

- Extramedullary Disease (approximately every 12 weeks, eg. Cycle 4, 7, 10): Required if positive at screening/ baseline as determined by Independent Adjudication Committee.
- Skeletal survey (Cycle ≥ 2): only required if clinically indicated or to confirm response according to IMWG criteria. CT/MRI scans can also be performed if clinically indicated or to confirm response according to IMWG criteria.
- PK (up to 10 cycles) and ADA (refer to [Section 1.7](#) and [Section 1.8](#))
- Biomarker/ Exploratory Studies:
 - Immune genetic determinants in peripheral blood: including Killer cell Ig-like receptors (KIR), HLA Typing and Fc γ R genes (Cycle 1 only).
 - Peripheral blood for soluble CD38 (Cycle 1 only).
 - Peripheral blood for Immune phenotyping (Cycle 1 and 3 only).

Administration of isatuximab

Isatuximab Safety Labs:

Should a isatuximab infusion associated reaction of Grade ≥ 2 occur, additional blood sampling during the AE is required for analysis of markers of potential tumor lysis syndrome (uric acid, lactate dehydrogenase [LDH], BUN, creatinine, potassium, phosphate, ionized or corrected calcium).

Bone marrow aspirates/biopsy will be collected in CR suspected patients for MRD analysis.

12.3.2 Day 2, 3, 4 of Cycle 1 of Phase I part

- PK (refer to [Section 1.7](#))

12.3.3 Day 8 and Day 22 of Cycle 1

The evaluations below are to be performed prior to IMP administration on Day 8 and 22 of Cycles 1 only.

- Clinical Examinations:
 - Physical Examination
 - Weight
 - Vital signs
(to be taken pre-infusion, mid-infusion (when half the volume is administered), and end-infusion on days of IMP administration. If the infusion rate changes because of an infusion-associated reaction, vital signs should be monitored every hour and at the end of the infusion.)
 - AE/ SAE assessment
 - Concomitant Medications

- Laboratory Assessments:
 - Hematology
 - Serum Chemistry
- PK and ADA (refer to [Section 1.7](#) and [Section 1.8](#))

Administration of isatuximab

Isatuximab Safety Labs (if \geq Grade 2 infusion associated reaction)

12.3.4 Day 15 of Each Cycle

The evaluations below are to be performed prior to IMP administration on Day 15 of each cycle unless otherwise indicated.

- Clinical Examinations:
 - Physical Examination (Cycle 1, 2, 3 only)
 - Weight
 - Vital signs
(to be taken pre-infusion, mid-infusion (when half the volume is administered), and end-infusion on days of IMP administration. If the infusion rate changes because of an infusion-associated reaction, vital signs should be monitored every hour and at the end of the infusion.)
 - AE/ SAE assessment
 - Concomitant Medications
- Laboratory Assessments:
 - Hematology
 - Serum Chemistry
 - Urinalysis: Quantitative urinalysis will be needed if hematuria is observed or clinically indicated.
 - In case of viral reactivation during study treatment (greater than $1 \log_{10}$ IU/mL increase in HBV DNA or reappearance of HBsAg or detection of HBV DNA in patients with resolved infection), ALT and AST will be closely monitored every month up to study treatment discontinuation. HBV DNA to be done as per specialist advice (Phase II part, Subsequent Cycles only).
- PK (refer to [Section 1.7](#) and [Section 1.8](#), up to 10 cycles)
- ADA (Cycle 1 only)

Administration of isatuximab

Isatuximab Safety Labs

12.4 END OF TREATMENT VISIT (TO BE PERFORMED 30 DAYS (+/- 7 DAYS) AFTER THE LAST ADMINISTRATION OF THE INVESTIGATION MEDICINAL PRODUCT)

- Inform to the registration center
- Clinical Examinations:
 - Physical Examination
 - Performance Status (ECOG)
 - Weight
 - Vital signs
 - AE/ SAE assessment
 - Concomitant Medications
- Laboratory Assessments:
 - Hematology
 - Serum Chemistry
 - If history of HBV infection is suspected, perform HBV-DNA test.
 - Urinalysis: Quantitative urinalysis will be needed if hematuria is observed or clinically indicated.
 - Serum Pregnancy Test
- Disease Assessment:
 - Myeloma-specific Lab Tests:
 - M-protein quantification (serum electrophoresis and immunofixation and 24-hour urine collection for Bence Jones protein with urine electrophoresis and immunofixation)
 - Serum free light chain levels
 - Serum β 2-microglobulin
 - Immunoglobulins: IgG, IgA, IgM, IgD and IgE
 - Corrected serum calcium
 - Extramedullary Disease (approximately every 12 weeks, eg. Cycle 4, 7, 10): Required if positive at screening/ baseline as determined by Independent Adjudication Committee. May be omitted at End of Treatment if conducted within 12 weeks.
- PK and ADA (refer to [Section 1.7](#) and [Section 1.8](#))
- Biomarker/ Exploratory Studies:
 - Immune phenotyping (peripheral blood sample)

12.5 FOLLOW-UP VISIT (TO BE PERFORMED 60 DAYS (+/- 7 DAYS) AFTER THE LAST ADMINISTRATION OF THE INVESTIGATION MEDICINAL PRODUCT)

- Inform to the registration center.
- Clinical Examinations:
 - AE/SAE Assessment (all ongoing related AE, ongoing SAE/AESIs, and new related AE/SAE/AESIs are to be followed up to resolution or stabilization)
 - Concomitant Medication (if for related AE, ongoing SAE/AESIs, and new related AE/SAE/AESIs)
 - The first new anticancer therapy after the last IMP administration.
- Disease Assessment:

Disease assessments during follow-up period are only required for patients with PR or better who have discontinued study treatment for reasons other than disease progression and have not yet started treatment with another anti-cancer therapy. Disease assessments will be done up to PD, initiation of further anti-cancer therapy or second cut-off date, whichever comes first. Patients will be followed every 4 weeks for progression during this period. Disease assessments required every 4 weeks is myeloma-specific lab tests. Extramedullary disease assessment is required approximately every 12 weeks or upon clinical suspicion of progressive disease. All imaging will be sent to a central imaging lab. A bone marrow aspiration and/or biopsy, skeletal survey are only required if clinically indicated to confirm response or progression according to IMWG criteria.

 - Myeloma-specific Lab Tests:
 - M-protein quantification (serum and 24-hours urine)
 - Serum β 2-microglobulin to be performed if clinically indicated
 - Immunoglobulins: IgG, IgA, IgM (IgD or IgE test to be performed if positive at baseline)
 - Corrected serum calcium
 - Serum and urine immunofixation and free light chain tests to be performed to confirm a CR and as clinically indicated.
 - Extramedullary Disease: Required if positive at screening/ baseline as determined by Independent Adjudication Committee.
- ADA (refer to [Section 1.7](#) and [Section 1.8](#)): if patient is positive for ADA or the sample is inconclusive, additional ADA samples are required every month (\pm 7 days) until sample is negative.

12.6 PERIOD POST 60 DAYS FOLLOW-UP PERIOD

- Clinical Examinations:
 - New anticancer therapy
 - AE/SAE Assessment (all ongoing related AE, ongoing SAE, and new related AE/SAEs are to be followed up to resolution or stabilization)
 - Concomitant Medication (if for related AE, ongoing SAE, and new related AE/SAEs)
- Survival Status:

Patients will also be followed for survival status approximately every 3 months from the date of last IMP administration until death or second cut-off date, whichever comes first. Every effort will be made to follow all patients. If survival follow-up is missed and is not obtained at the time of the scheduled interval, it should be obtained immediately. For subsequent survival follow-up, the patient should be contacted at the original scheduled survival follow-up interval. If the patient is unable to visit the clinical center, the follow-up may be done via phone from the Investigator or designee to the patient or the patient's caregiver or a family member.
- Disease Assessment:

Disease assessments during follow-up period are only required for patients with PR or better who have discontinued study treatment for reasons other than disease progression and have not yet started treatment with another anti-cancer therapy. Patients will be followed every 4 weeks for progression during this period. Disease assessments required every 4 weeks is myeloma-specific lab tests. Extramedullary disease assessment is required approximately every 12 weeks or upon clinical suspicion of progressive disease. All imaging will be sent to a central imaging lab. A bone marrow aspiration and/or biopsy, skeletal survey are only required if clinically indicated to confirm response or progression according to IMWG criteria. Disease assessments not required once patient starts treatment with another anti-cancer therapy.

 - Myeloma-specific Lab Tests:

(For patients with PR or better who have discontinued study treatment for reasons other than disease progression and have not yet started treatment with another anti-cancer therapy only)

 - M-protein quantification (serum and 24-hours urine)
 - Serum β 2-microglobulin to be performed if clinically indicated
 - Immunoglobulins: IgG, IgA and IgM (IgD or IgE test to be performed if positive at baseline)
 - Corrected serum calcium
 - Serum and urine immunofixation and free light chain to be performed to confirm a CR and as clinically indicated.
 - Extramedullary Disease: Required if positive at screening/ baseline as determined by Independent Adjudication Committee.

- ADA:
If patient is positive for ADA or the sample is inconclusive, additional ADA samples are required every month (\pm 7 days) until sample is negative.

12.7 POST SECOND ANALYSIS CUT-OFF PERIOD

If a patient continues to benefit from the treatment after the second analysis cut-off date, the patient can continue study treatment. Such patients will be followed until 60 days after the last administration of the IMP and will continue to undergo select study assessments. The following information will be collected: IMP(s) administration, IMP-related AEs, and any SAEs.

Procedures and data collection for patients still receiving isatuximab at the time of the second analysis cutoff date will be as follows:

- Clinical Examinations:
 - Ongoing related AE(s) and ongoing SAE(s), up to stabilization or resolution,
 - New SAE(s), new related AE(s),
 - Reason for end of treatment upon isatuximab discontinuation
- ADA:
If patient is positive for ADA or the sample is inconclusive, additional ADA samples are required every month (\pm 7 days) until sample is negative.
- Administration of isatuximab

Patients with ongoing related AE(s) and ongoing SAE(s) after treatment discontinuation will be followed until stabilization or resolution of the AE/SAE.

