15. Serum chemistry includes: SGOT (AST), SGPT (ALT), bilirubin (total and direct), alkaline phosphatase, lactate dehydrogenase (LDH), fasting glucose, sodium, potassium, magnesium, chloride, calcium, corrected serum calcium, phosphate, uric acid, blood urea nitrogen (BUN), serum creatinine and eGFR (Revised equations for eGFR in Japanese), albumin and total protein. To be done at screening, then prior to pre-medication and IMP administration on Day 1, Day 8, Day 15 and Day 22 of Cycle 1 and on Day 1 and Day 15 of every subsequent cycle, at the EoT visit and as clinically indicated.
16. Coagulation: To be done at screening and then as clinically indicated. Coagulation includes: Prothrombin time (PT) or international normalized ratio (INR) and activated partial thromboplastin time (aPTT).
17. Urinalysis includes: blood, protein, glucose, pH, ketones, bilirubin, leucocytes, nitrites and specific gravity. To be done at baseline, on Day 1 and Day 15 of each cycle, EoT, and if clinically indicated. Quantitative urinalysis will be needed if hematuria is observed or clinically indicated.
18. Pregnancy Test: Women of child bearing potential must have a negative serum pregnancy test result within 7 days prior to first IMP administration and at the EoT visit. Urine test can be used at Day 1 of each subsequent cycle.
19. HBc-Ab, HBs-Ab test: If HBc-Ab and/or HBs-Ab positive at baseline, Hepatitis B Virus (HBV)-DNA test is required prior to registration. If history of HBV infection is suspected, monitoring of HBV-DNA is recommended on Day 1 of each cycle, EoT and if clinically indicated.
20. Once at any time if HBV status unknown before treatment started and to be repeated if clinically indicated.
21. Myeloma-specific Lab Tests: serum electrophoresis, immunoglobulin assay, corrected serum calcium and 24-hour urine collection for Bence Jones protein to be performed at baseline prior to administration, prior to each cycle thereafter and at time of study discontinuation (if last tests were >4 weeks). Serum β 2 microglobulin to be performed at baseline prior to administration, EoT and if clinically indicated. Immunofixation and free light chain tests to be performed at baseline prior to administration, EOT, if CR is suspected and if clinically indicated.

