34. Survival status: Patients will also be followed for survival status approximately every 3 months (\pm 14 days) from the date of last IMP administration until death or second cutoff date, whichever comes first. Every effort will be made to follow all patients. If survival follow-up is missed and is not obtained at the time of the scheduled interval, it should be obtained immediately. For subsequent survival follow-up, the patient should be contacted at the original scheduled survival follow-up interval. If the patient is unable to visit the clinical center, the follow-up may be done via phone from the Investigator or designee to the patient or the patient's caregiver or a family member.
35. Adverse Event/Serious AE Reporting: All AEs, including events of new onset as well as worsening of baseline signs and symptoms are to be reported from the signing of the informed consent to 30 days following the last administration of study treatment. After the 30 day follow-up all ongoing related AEs, ongoing SAE/AESIs regardless of relationship and new related AE/SAE/AESIs are to be followed to resolution or stabilization.
36. Post second analysis cut-off period, only AE/SAE reporting will be collected

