6.6.3 Guidance in case of hepatitis B reactivation occurring under study treatment

Patient still on treatment at the time of amended protocol 05 will be tested for HBV serology and HBV viral DNA once at any time if HBV status was unknown before treatment started; test will be repeated if clinically indicated.

In case of viral reactivation during study treatment (greater than $1 \log_{10}$ IU/mL increase in HBV DNA or reappearance of HBsAg or detection of HBV DNA in patients with resolved infection) study treatment will be held and specialist consulted for initiation of anti-viral treatment and monitoring of the patient. Resolved infection means previous known history of acute or chronic hepatitis B or the presence of total anti-HBc Ab with/without anti-HBs Ab; HBsAg negative; undetectable serum HBV DNA; and normal ALT levels. Restart of study treatment should be

agreed between the Sponsor, the Investigator and specialist (hepatologist) if infection is controlled. ALT and AST will be closely monitored every month up to study treatment discontinuation. HBV DNA to be done as per specialist advice.

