E 09. Neuropathy Grade ≥ 3 or painful peripheral neuropathy Grade ≥ 2

E 10. History of significant cardiovascular disease unless the disease within the past 6 months is well-controlled.

Significant cardiac diseases include,

- Second/third degree atrioventricular block
- Significant ischemic heart disease
- QTc interval >450 msec at baseline (read by local cardiologist)
- Poorly controlled hypertension
- Congestive heart failure of NYHA Class III or worse (marked limitation of physical activity comfortable at rest, but less than ordinary activity causes fatigue, palpitation, dyspnea or anginal pain)
- LVEF <45%
Significant ischemic heart disease (eg, angina) and poorly controlled hypertension are defined as medical conditions that, in the opinion of the Investigator or Sponsor, may interfere with patient's participation in the study, affect the interpretation of the study results, or patient's safety.

E 11. Previously received an allogenic stem cell transplant.

- E 12. Diagnosed Crow-Fukase (POEMS) syndrome
OR
plasma cell leukemia.
- E 13. Patients with known or suspected amyloidosis.
- E 14. Patients with Waldenstrom's macroglobulinemia
OR
Multiple myeloma IgM subtype.
- E 15. Patients with active infection requiring systemic antibiotics, antivirals or antifungals within 2 weeks prior to the first dose of IMP (except when used for chronic prophylaxis).
- E 16. Known human immunodeficiency virus (HIV) or active hepatitis B or C viral infection.
- E 17. Serious psychiatric illness, active alcoholism, or drug addiction that may hinder or confuse follow-up evaluation.
- E 18. Any medical conditions that, in the Investigator's opinion, would impose excessive risk to the patient (eg, poorly controlled diabetes or poorly controlled hypotension).
- E 19. Hypersensitivity or history of intolerance to boron or mannitol, sucrose, histidine (as base and hydrochloride salt) and polysorbate 80 or any of the components of study therapy that are not amenable to pre-medication with steroids and H2 blockers or would prohibit further treatment with these agents.
- E 20. Female subjects who are pregnant or lactating.
If a female who stopped lactating before entering in the study, the female must stop lactating from the day of the first IMP administration until 6 months after the last administration of the IMP.

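### Read as written, Section 12.7 and flowchart footnote 36 drop the Day 1 HBV-DNA test after the second cut-off, in conflict with Section 12.3.1 and footnote 19, which set it for every cycle

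*Protocol*

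**What the plan says.** **After the second cut-off.** Protocol Section 12.7 says that patients who keep benefiting may stay on isatuximab and will have selected assessments only. It then states: "Procedures and data collection for patients still receiving isatuximab at the time of the second analysis cutoff date will be as follows". The list covers ongoing and new adverse events of defined types, the reason for ending treatment, anti-drug antibodies (ADA) and isatuximab administration. ADA is the only laboratory item. Footnote 36 (Section 1.6), attached to the Subsequent Cycles column of both study flowcharts, reads: "Post second analysis cut-off period, only AE/SAE reporting will be collected".

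**The HBV-DNA test.** Section 12.3.1 instructs: "If history of HBV infection is suspected, perform HBV-DNA test on Day 1 of each cycle". Footnote 19 is softer: "If history of HBV infection is suspected, monitoring of HBV-DNA is recommended on Day 1 of each cycle, EoT and if clinically indicated". Section 12.2 also uses the softer form: "If history of HBV infection is suspected, monitoring of HBV-DNA is recommended on Day 1 of each cycle". None of the three gives an end date.

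**Who qualifies.** Exclusion criterion E 16 covers "Known human immunodeficiency virus (HIV) or active hepatitis B or C viral infection". A patient with antibody evidence of past infection is tested rather than excluded: "If HBc-Ab and/or HBs-Ab positive at baseline, Hepatitis B Virus (HBV)-DNA test is required prior to registration".

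**What follows from reactivation.** Section 6.6.3 defines reactivation by HBV-DNA or HBsAg results. It then requires treatment to be held, a specialist to be consulted, and ALT and AST to be followed monthly. It also adds a single test: "Patient still on treatment at the time of amended protocol 05 will be tested for HBV serology and HBV viral DNA once at any time". That test applies only where HBV status was unknown before treatment, with repeats if clinically indicated.

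**The concern.** Two parts of the protocol give different instructions for the same patient. Under 12.3.1, a patient with suspected past hepatitis B has an HBV-DNA test at the start of every cycle for as long as treatment lasts. Under 12.7 and footnote 36, the same patient, still receiving the same drug, has no scheduled HBV or liver test once the second cut-off has passed.

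What is at stake is patient safety. The treatment hold in 6.6.3 is triggered by a virological result. A site that follows 12.7 literally has no scheduled test that would produce one. It would depend on a clinical event or on someone deciding that a test was indicated. Amendment 05 was issued because hepatitis reactivation had been identified as a risk. Its change table lists revisions to the flowchart, the footnotes, 6.6.3, 12.3.1 and 12.3.4 for that reason, but none to 12.7.

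**Working it through.** No power, alpha or sample-size figure bears on this point. The check compares the texts and then does some date arithmetic. Appendix J (the amendment history) is used only to date events and for stated purpose, not as text in conflict with the current protocol.

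**1. The texts side by side, for a patient with suspected prior HBV who is still on isatuximab**

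| Source | Day 1 HBV-DNA | End date |
|---|---|---|
| 12.3.1 | ordered, each cycle | none |
| Footnote 19 | recommended, each cycle | none |
| 12.2 | recommended, each cycle | none |
| 12.7 | not in the list of procedures | applies from the second cut-off |
| Footnote 36 | excluded by its restrictive wording | applies from the second cut-off |

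**2. Does absence from 12.7 stop a test?** Section 12.3.1 also still lists the myeloma-specific laboratory tests for Day 1 of each cycle, again without an end date. Appendix J records that Amendment 04 ended those tests after the cut-off by deleting them from 12.7. So 12.7 works as the governing list, and a test missing from it is stopped even though 12.3.1 still carries it.

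**3. What else could detect reactivation?**
- The single test in 6.6.3 and footnote 20 is for unknown HBV status. It sets no schedule for patients already known to be antibody-positive.
- Repeat HBV testing if clinically indicated remains possible but is unscheduled.
- AST and ALT on Day 1 and Day 15 (footnote 15) are a recurring but indirect liver signal, and they too are absent from 12.7.
- The monthly ALT/AST in 6.6.3 starts only after reactivation has been found.
- Under 10.5.1, a laboratory abnormality is an adverse event only if it leads to discontinuation or dose modification, is serious, or is an event of special interest. A silent viral rise need not be reported.

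The Day 1 HBV-DNA test is therefore the only scheduled per-cycle virological test of a 6.6.3 criterion.

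**4. Had the 12.7 period begun by Amendment 05?** Inputs: first cut-off 4 months and second cut-off 20 months after the last patient's first dose (6.7.2; the synopsis says approximately); Amendment 04, dated 14 December 2018, refers to results at the first analysis; Amendment 05 is dated 15 July 2020.
- First cut-off: no later than 14 Dec 2018.
- Last first dose: 14 Dec 2018 − 4 months = no later than 14 Aug 2018.
- Second cut-off: 14 Aug 2018 + 20 months = no later than 14 Apr 2020.
- 14 Apr to 15 Jul 2020 = 92 days before Amendment 05.
- Assumed slippage of one month on each interval, in the unfavourable direction: 14 Dec 2018 − 3 months = 14 Sep 2018; + 21 months = 14 Jun 2020; 31 days before Amendment 05.

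**5. Does the single test in 6.6.3 fill the gap?** HBc-Ab and HBs-Ab screening came in with Amendment 01, dated 13 May 2016. The Phase 1 SAP, Section 1.6, places the first enrolment in September 2016. From 13 May to 1 September 2016 is 111 days, so few or no patients should have had unknown status. The patients of interest here are those whose past infection was already suspected.

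**6. Testing load.** 365 / 28 = 13.0 tests per patient-year.

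**The case against.** The strongest reply is that the protocol shows 12.3.1 was meant to stay in force. On the dates above, every patient still on drug at Amendment 05 was already past the second cut-off. Yet that amendment put new HBV text into 12.3.1 and 12.3.4 for subsequent cycles. It also added an HBV test mark to the Phase II flowchart, apparently in the column that carries footnote 36. Those edits make sense only if the sections still operate after the cut-off.

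Nor can the restrictive texts be complete. Footnote 36 allows only adverse event reporting, while the PK flowchart footnotes allow only ADA samples for the same period. Section 12.7 omits body weight, although dosing is per kilogram, and it omits pre-medication. It can be read as setting the scope of data capture. Finally, the HBV-DNA test is only recommended in two of its three statements.

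Much of this stands. It shows that the sponsor probably intended monitoring to continue and that a careful site could reasonably continue it. It also shows that footnote 36 alone does not settle the matter. It does not remove the conflict, because the wording of 12.7 covers procedures as well as data collection, and that wording was left in place. Appendix J says that Amendment 04 confined the post-cut-off period to safety observation. HBV-DNA monitoring is safety observation and is not among the recorded deletions, which supports restoring it.

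**Conclusion.** The conflict is real and minor. Read as written, 12.7 and footnote 36 remove a scheduled safety test that 12.3.1 and footnote 19 continue without limit, and patients who need it may enrol. A correction is a cheap gain in patient safety.

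Some stronger readings are tempting, but the documents do not support them:
- **That the test is the only means of detecting reactivation.** Testing if clinically indicated and routine AST/ALT are weaker back-ups, although AST/ALT has the same gap in 12.7.
- **That the 6.6.3 protections lapse at the cut-off.** They apply on their own terms during study treatment. What is missing is the scheduled result that would trigger them.
- **That the sponsor chose to stop the test.** Nothing says so. The test was added at the regulator's suggestion, citing a guideline that recommends monthly HBV-DNA (Appendix J, Amendment 01).
- **That patients were left unmonitored.** The documents state neither how many patients remained on drug nor how many had suspected prior HBV. The number affected may be zero.

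The timing is an inferred upper bound that assumes the planned intervals were roughly kept, since neither the last first dose nor the actual cut-off date is given. The textual conflict does not depend on it. No efficacy endpoint or analysis is affected.

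**What to change.** Add one sentence to 12.7: where prior HBV infection is suspected, HBV-DNA with ALT and AST is measured on Day 1 of each cycle for as long as isatuximab is given, and Section 6.6.3 continues to apply. Add a matching exception to footnote 36. The scope of the Phase I and Phase II parts need not change.

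The cost is a short wording change with IRB handling under Section 17. The testing load is about 13 HBV-DNA tests per patient-year, with ALT/AST at the same visits, in the few patients, possibly none, who qualify. These tests are already described for Day 1 in 12.3.1 and footnote 15.
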